**30 days (between 30 to 45 days post implant)**

- Clinical assessment
- TTE
- 12 lead ECG
- Modified Rankin Score
- KCCQ
- EQ-5D
- Anti-thrombotic medications
- INR (for subjects on VKA)
- Adverse events

**One Year (between 365 and 395 days post implant)**

- Clinical assessment
- TTE
- Modified Rankin Score
- KCCQ
- EQ-5D
  - Anti-thrombotic medications
  - INR. (for subjects on VKA)
- Adverse events

**Two Year (between 730 and 760 days post-implant)**

- Clinical assessment
- TTE
- Modified Rankin Score
- KCCQ
- Anti-thrombotic medications
- INR. (for subjects on VKA)
- Adverse events

**Annually from 3 years through 5 years (between implant anniversary date and +/-60 days after)**

- Clinical assessment
- TTE
- Modified Rankin Score
- KCCQ

- Anti-thrombotic medications
- INR (for subjects on VKA)
- Adverse events

**6 years, 8 years and 9 years (between implant anniversary date and +/-60 days after)**

- Adverse events

**7 years and 10 years (between implant anniversary date and +/-60 days after)**

- Clinical assessment
- TTE
- Adverse events

**Other Evaluations**

- A Modified Rankin Score assessment should be conducted at 1 and 3 months following any suspected or confirmed stroke event.

**Visit Windows**

Baseline	Within 12 weeks prior to submitting to the screening committee (except for MDCT and coronary arteriography) as noted in Section 3.3.9)
Discharge	Discharge from index procedure or 7 days post implant, whichever comes first
30 Days	Between 30 and 45 days post implant
1 Year	Between 365 and 395 days post implant
2 Year	Between 730 and 760 days post-implant
3 – 10 Years	Between implant anniversary date and +/-60 days after

**Table 3. Summary of visit schedule and required evaluations through 5 years**

Evaluation/Visit	Baseline (Pre-Implant)	Implant	18 Hrs to 7 Days (Device Success)	Discharge	30 Days	1 Year	Annual (through 5 Years)
Clinical Assessment	X			X	X	X	X
Adverse Events	X	X	X	X	X	X	X
Coronary Arteriography	X						
MDCT	X						
TTE	X		X		X	X	X
12-lead ECG	X			X	X		
Modified Rankin Score	X			X	X	X	X
Hemodynamics		X					
Aortography		X					
Complete Blood Count	X						
I.N.R.				X	X	X	X
Anti-thrombotic Medications	X			X	X	X	X
KCCQ	X				X	X	X
EQ-5D	X				X	X	

**Table 4. Summary of visit schedule and required evaluations from 6 through 10 years**

	Years 6, 8, and 9 	Years 7 and 10
Clinical Assessment		X
Adverse Events	X	X
TTE		X

 Follow-up visits at years 6, 8 and 9 may be conducted remotely (eg, phone call)

## 8.2. Screening

The process of patient screening is as follows:

1. Patients identified by or presented to the study site with aortic stenosis will be screened by the investigative team for the criteria described in section 7.0 Selection of Subjects, using available medical records, including relevant imaging studies previously performed for diagnostic purposes.
2. If the patient is deemed a potential candidate for the study the investigational status of the Medtronic TAVR System and all aspects of the study will be explained to the patient.
3. If the patient agrees to participate, written informed consent will be obtained. This will be considered the point of enrollment, and the subject will be assigned a Subject ID number.
4. The subject will undergo transthoracic echocardiography (TTE) to assess his/her degree of aortic stenosis.
5. Subjects who meet the criteria for aortic stenosisi will undergo:
  - a. Multi-Detector Computed Tomography (MDCT) of their peripheral vasculature and aortic annulus to confirm bicuspid aortic valve anatomy and assess anatomic suitability for the Medtronic TAVR,  
**AND**
  - b. Local Heart Team assessment to determine his/her operative risk profile for SAVR
6. If the local Heart Team considers the subject anatomically suitable for implantation and at low risk for SAVR, the subject's clinical information will be submitted to the Screening Committee. The Heart Team assessment must be documented. The following information should be submitted to the Screening Committee:
  - Clinical assessments including STS-PROM, medical history and co-morbidities
  - TTE data on degree of aortic stenosis
  - MDCT data on anatomical suitability and bicuspid aortic valve anatomyii
7. The Screening Committee will review the clinical information to confirm the eligibility of the subject for implantation.
8. Concomitant percutaneous coronary intervention (PCI)iii with TAVR is allowed; however, staging is left to the discretion of the operator. Elective intervention/repair of the mitral or tricuspid valve is not allowed during the TAVR procedure.
9. Implantation should occur within 90 days of Screening Committee approval.

## 8.3. Role of Sponsor Representatives

Representatives from Medtronic will provide confirmation of anatomical criteria prior to implant of each subject. In addition, representatives from Medtronic may provide technical support during the implant

---

i If a subject has balloon aortic valvuloplasty after their qualifying TTE, they must have repeat TTE to confirm he/she meets criteria for severe aortic stenosis as described in Section 7.3 prior to submission to the screening committee.

ii Anatomical suitability will be confirmed by Medtronic Screening Lab. Information on MDCT procedures and sizing recommendations is provided in Appendix II, Section 4.0.

iii Index PCI should be performed at the TAVR implanting center; index PCI operators will be considered investigators.

procedures to the implanting physicians and study site staff relative to the use of the investigational devices.

## **8.4. Subject Consent**

### **8.4.1. Informed Consent**

Prior to enrolling in the study, patients should be fully informed of the details of study participation as required by applicable regulations, the site's IRB and by Medtronic. Informed consent must be obtained from each patient prior to conducting any protocol-induced activities beyond standard of care, by using the informed consent form (ICF) approved by that site's IRB and by Medtronic. The ICF must be signed and dated by the patient and by the person obtaining the consent. Any additional persons required by the site's IRB to sign the informed consent form must also comply.

Prior to the patient signing the ICF, the investigator or authorized designee will fully explain to the patient the nature of the research, study procedures, anticipated benefits, and potential risks of participation in the study. The investigator or delegate will allow adequate time for the patient to read and review the consent form and to ask questions. Signing the ICF serves to document the written and verbal information that the investigator or authorized delegate provides to the patient, the patient's understanding of the information, and his/her agreement to participate. The investigator or authorized delegate must document in the patient's medical records that the patient was consented and the date on which the consent was obtained. The original signed consent form will be retained in the patient's study records and a copy of the informed consent will be provided to the patient.

Patients should give written consent before undergoing any protocol-required testing. However, if any of protocol-required baseline/screening evaluations (eg, echocardiography, MDCT, coronary arteriography, lab work) have been performed for clinical diagnostic purposes prior to consenting, they can be used as the protocol-required exams, provided they were obtained within the protocol-required time windows and contain the necessary information.

### **8.4.2. Revisions in Patient Information and Informed Consent Form**

Medtronic will inform the investigators whenever information becomes available that may be relevant to the subject's continued participation in the study. The revised information will be sent to the investigator for approval by the IRB/EC. After approval by the IRB/EC, a copy of this information must be provided to the participating subjects, and the informed consent process as described above needs to be repeated. The investigator or his/her designee should inform the subject in a timely manner.

## **8.5. Subject Disposition**

Sites will maintain a log of subjects consented, date attempted and implanted, as well as the Subject ID numbers assigned to each patient. Subjects who are consented but are not taken to the procedure room for implantation will be exited from the study and will not be followed beyond the date of study exit.

Subjects who are taken to the procedure room for implantation but do not receive a TAV for any reason will be followed for safety events for 30 days post-index procedure. Subjects that have their TAV bioprosthesis explanted will be followed for safety events for 30 days after the explant.

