#### Analysis Sets

There are two different analysis sets that are defined for this study. The primary analysis will be the “attempted implant” analysis. Analysis sets used for each objective are defined under the corresponding objective section. The analysis subsets are defined as follows:

**Attempted implant set:** The attempted implant set consists of all enrolled subjects with an attempted implant procedure, defined as when the subject is brought into the procedure room and any of the following have occurred: anesthesia administered, vascular line placed, TEE placed or any monitoring line placed. Subjects will be analyzed according to their first attempted procedure (TAVR). Day 0 is date of first attempted procedure.

**Implanted set:** The implanted set consists of all the attempted implant subjects who are actually implanted with the TAV. Day 0 is date of first attempted procedure.

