## 12.9. Number of Subjects and Investigational Devices, Study Duration

This study will involve up to 150 total attempted implant subjects among all active sites. No site will implant more than 20% of the total number of attempted subjects without prior authorization from Medtronic. Subjects who exit from the study after implantation will not be replaced.

Subjects will be consented for follow-up through 10 years. The enrollment period is estimated to be between 12 to 24 months; therefore, the estimated total duration of the study (first subject enrolled to last subject completing his/her last follow-up exam) is estimated to be 12 years. The number of investigational TAVR systems used in the study is estimated to be between 150 and 200 (based on sample size).

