7.2. General Methodology

Descriptive statistics will be used to report study data. For continuous variables (eg. age), the mean, median, standard deviation, minimum, maximum and interquartile ranges (IQR) will be presented. For categorical variables, the number and percentage of subjects in the category of interest will be presented.

For time to event variables, Kaplan-Meier analyses of event rates at 30 days, 1 year and annually through end of study will be presented. For these analyses, the time points will correspond to 30 days, 365 days, 730 days, 1095 days, 1460 days, 1825 days, 2190 days, 2555 days, 2920 days, 3285 days and 3650 days post implantation respectively. At each time point with data, the product limit estimate of the event, the number of subjects at risk, the number of subjects with events, and the 95% confidence interval will be presented. For subjects without an event, the date of censoring will be the latest date of all follow-up visits, assessments, and events (including death).

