7.4. Handling of Missing, Unused, and Spurious Data and Dropouts

Every effort will be undertaken to minimize missing data. In time-to-event outcomes drop-outs will be censored at the time of discontinuation, consistent with the Kaplan-Meier approach.

Missing (accidentally, due to withdrawal, missing follow-up or loss to follow-up, etc.), unused and spurious data will remain identifiable in the database. Data from subjects that cannot be analyzed for a specific variable will be displayed as missing in the relevant summary tables. In this manner, all data for a specific variable are accounted for. Unless otherwise specified, no statistical techniques will be used to impute missing data. The number of subjects included in each analysis will be reported so that the reader can assess the potential impact of missing data.

In the case of partial dates, if only the month and year are known, the event or assessment will be analyzed as if it occurred on the 15th of that month. If only the year is known, the event or assessment will be analyzed as if it occurred on June 30th of that year. These resolutions of partial dates are subject to the restrictions that events must occur no earlier than the procedure date.

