7.9.3. Additional Outcome Measures

1. All-cause mortality at one year, and annually through 10 years

Event rate estimates will be provided at 1 year and annually thereafter up to 10 years for the attempted implant set. The outcome is descriptive including Kaplan-Meier rates and no statistical hypothesis test is specified.

2. All stroke (disabling and non-disabling) at one year, and annually through 10 years

Event rate estimates will be provided at 1 year and annually thereafter up to 10 years for the attempted implant set. The outcome is descriptive including Kaplan-Meier rates and no statistical hypothesis test is specified.

3. New permanent pacemaker implantation at 30 days

Event rate estimates will be provided at 30 days for the attempted implant set. The outcome is descriptive including Kaplan-Meier rates and no statistical hypothesis test is specified.

4. Myocardial Infraction at 30 days

Event rate estimates will be provided at 30 days for the attempted implant set. The outcome is descriptive including Kaplan-Meier rates and no statistical hypothesis test is specified.

5. Life-threatening bleeding at 30 days, one year, and annually through 10 years

Event rate estimates will be provided at 30 days, 1 year and annually thereafter up to 10 years for the attempted implant set. The outcome is descriptive including Kaplan-Meier rates and no statistical hypothesis test is specified.

6. Prosthetic valve endocarditis at 30 days, one year, and annually through 10 years

Event rate estimates will be provided at 30 days, 1 year and annually thereafter up to 10 years for the attempted implant set. The outcome is descriptive including Kaplan-Meier rates and no statistical hypothesis test is specified.

7. Prosthetic valve thrombosis at 30 days, one year, and annually through 10 years

Event rate estimates will be provided at 30 days, 1 year and annually thereafter up to 10 years for the attempted implant set. The outcome is descriptive including Kaplan-Meier rates and no statistical hypothesis test is specified.

8. Valve-related dysfunction requiring repeat procedure at 30 days, one year, and annually through 10 years

Event rate estimates will be provided at 30 days, 1 year and annually thereafter up to 10 years for the attempted implant set. The outcome is descriptive including Kaplan-Meier rates and no statistical hypothesis test is specified.

9. Repeat hospitalization for ascending aorta disease at 30 days, one year, and annually through 10 years

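### Follow-up stops 30 days after a failed implant or an explant, yet mortality and stroke are estimated to 10 years on a set that includes these subjects

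*Protocol*

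**What the plan says.** **Follow-up.** Protocol 8.5 (Subject Disposition) deals with two groups. Subjects taken to the procedure room who "do not receive a TAV for any reason will be followed for safety events for 30 days post-index procedure" form the first. The second is covered by the sentence "Subjects that have their TAV bioprosthesis explanted will be followed for safety events for 30 days after the explant".

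**Analysis set.** Protocol 12.2 and SAP 7.1.3 make the attempted implant set the primary one, "defined as when the subject is brought into the procedure room and any of the following have occurred": anaesthesia, or placement of a vascular line, a TEE probe or a monitoring line. A subject who receives no valve belongs to it, and an explant does not remove a subject from it.

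**Estimates.** Protocol 12.7 uses this set for safety and quality-of-life outcomes. For all-cause mortality and all stroke, SAP 7.9.3 states "Event rate estimates will be provided at 1 year and annually thereafter up to 10 years for the attempted implant set", using Kaplan-Meier rates.

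**Censoring.** SAP 7.2 censors event-free subjects at their last recorded contact. SAP 7.4 adds: "In time-to-event outcomes drop-outs will be censored at the time of discontinuation, consistent with the Kaplan-Meier approach". By default nothing is imputed, and no sensitivity analysis is planned for these two groups.

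**Other statements on follow-up.** Protocol 5.1 and 8.15 describe 10 years for subjects in general, and 12.9 says "Subjects will be consented for follow-up through 10 years". None of them mentions the exception in 8.5. Protocol 12.1, by contrast, times the final analysis by implanted subjects only.

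**The concern.** The set that is analysed to 10 years is wider than the set that is followed to 10 years. Kaplan-Meier gives a censored subject the future risk of those still under observation. That is reasonable when censoring is unrelated to prognosis. Here the protocol itself triggers the censoring, because the procedure failed or the valve had to come out, and either event may plausibly go with a different later risk.

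If these subjects do worse, the long-term mortality and stroke rates will be somewhat too low, under a label that suggests every attempted subject is represented. Once contact stops, the missing outcomes are hard to recover.

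**Working it through.** **The plan's own figures.** The only precision figures in the documents are in SAP Table 2. Exact binomial 95% intervals reproduce them: 4/150 gives 0.73% to 6.69% (stated 0.7%, 6.7%), and 142/150 gives 89.76% to 97.67% (stated 89.8%, 97.7%). Nothing comparable is given for the 10-year outcomes, so the size has to be built up.

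**Step 1: how many non-implants?** SAP Table 1 lists subjects and systems implanted by study. Taking the difference as the number not implanted:

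- Subjects: 391 + 301 + 60 + 60 = 812.
- Systems implanted: 391 + 297 + 60 + 60 = 808.
- Difference: 4, all in the Evolut R IDE row. 4/812 = 0.49% (exact 95% interval 0.13% to 1.26%).
- In 150 subjects: 150 × 4/812 = 0.7 (0.2 to 1.9).
- At the Evolut R IDE rate alone: 150 × 4/301 = 2.0.
- The first row reports its safety rate over 394 rather than 391. If the extra 3 were also non-implants, the figure is 150 × 7/815 = 1.3, inside the same range.

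The documents give no explant rate.

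**Step 2: effect on the Kaplan-Meier rate.** Let k of 150 subjects be censored at about day 30, let p be mortality in those still followed, and q the true mortality in the k. Kaplan-Meier reports about p. The true rate is [(150 − k)p + kq]/150. The understatement is therefore

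k(q − p)/150.

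**Step 3: put the numbers in.** The documents do not give q − p. Assume 20 to 30 percentage points at 10 years.

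| k | Basis | q − p = 20 points | q − p = 30 points |
|---|---|---|---|
| 0.7 | 4/812 | 0.10 | 0.15 |
| 2 | 4/301 | 0.27 | 0.40 |
| 5 | assumed, with explants | 0.67 | 1.00 |
| 8 | assumed, with explants | 1.07 | 1.60 |

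Only the first two rows take k from the documents. The last two are scenarios.

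**Step 4: limit of the formula for explants.** It treats every affected subject as leaving at about day 30. An explanted subject is observed until 30 days after the explant, which may be years later, and any death up to then is counted. The formula therefore tends to overstate the explant part.

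**Step 5: compare with sampling error.** Assuming 10-year mortality of 25% to 55% and 150 subjects, the 95% half-width is 1.96 × √(0.25 × 0.75/150) = 6.9 points to 1.96 × √(0.55 × 0.45/150) = 8.0 points. The understatement is small beside that.

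**The case against.** **The failures are not lost.** A reader might infer that the events most informative about durability, or the worst outcomes, drop out. The documents do not support that. Valve dysfunction needing a repeat procedure includes surgical replacement (Protocol Appendix V) and is estimated to 10 years. Explants are tabulated in disposition (SAP 7.1.1), and an explant pathology laboratory is used (Protocol 15). Deaths and strokes within 30 days of the failed attempt or the explant are followed. What can be lost is what happens after that. This objection stands.

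**The direction is not proven.** Placing a monitoring line is enough to enter the set, so a harmless cancellation counts. All subjects have an indication for surgery at a predicted mortality below 3%, so some may go on to surgery and do well. A favourable bias is likely, not certain.

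**Larger sizes are not supported.** One could apply the 50% two-year mortality that Protocol 3.1 gives for untreated symptomatic patients. At a constant hazard this is 82% at 5 years. With eight subjects and p = 10%, the understatement is 8 × (0.82 − 0.10)/150, about 4 points. But nothing says these subjects go untreated, and the eight is assumed.

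**The study's main conclusion is not touched.** The primary objective is judged at 30 days, non-implanted subjects are followed to day 30, and device success uses the implanted set. A reader might still worry about disabling stroke, which needs a 90-day modified Rankin score. Protocol 8.1 asks for that score at 1 and 3 months after any stroke without exception, so the documents do not show that it would be missed. The reconciliation should confirm that this rule applies to non-implanted subjects.

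**Exit is inferred.** Protocol 8.5 uses the word only for subjects never taken to the procedure room. For the other two groups, an end to follow-up at 30 days is the natural reading, but not the only one. That ambiguity is itself a reason to reconcile the text.

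The mismatch between the set followed and the set analysed survives all of this.

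**Conclusion.** The inconsistency is real. Read as written, Protocol 8.5 leaves later deaths and strokes of non-implanted and explanted subjects out of estimates that SAP 7.9.3 assigns to the attempted implant set, and the reason for censoring is plausibly prognostic.

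The effect is probably a slight understatement. For non-implants it is about 0.1 to 0.4 points of 10-year mortality, resting on 0.7 to 2 affected subjects from SAP Table 1 and an assumed excess mortality of 20 to 30 points. Explants would add an amount that the documents do not allow one to estimate; 0.7 to 1.6 points is what 5 to 8 exits in total would give, and is a scenario only.

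The affected results are additional descriptive outcomes. The 30-day mortality result and the device success rate are unaffected. This is a cheap improvement, not a threat to the primary results.

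**What to change.** Reconcile Protocol 8.5 with Protocol 5.1, 8.15 and 12.1 and with SAP 7.9.3:

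- **Protocol 8.5:** continue remote contact for vital status, stroke and hospitalization through year 10 for every attempted-implant subject, including those without an implant or with an explant. Omit the valve-specific echo visits for them.
- **Protocol 12.1:** time the final analysis by all attempted-implant subjects.
- **SAP 7.2, 7.4 and 7.9.3:** state that non-implant and explant are not censoring events for mortality and stroke.
- **Reporting:** give the number of subjects in each of the two groups and how many were lost afterwards.

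Cost: amended wording and a few extra telephone contacts a year for a handful of subjects, with no added procedures. Remote visits are already allowed at years 6, 8 and 9, vital-status contact is already expected after a missed visit (Protocol 8.11), and subjects are to be consented for 10 years. Whether the consent form covers continued contact in these two groups should be checked.

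If follow-up is nevertheless to stop, the SAP should say that the long-term rates rest on censoring these subjects, report how many there were, and add best-case and worst-case bounds.
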